7.5.2. Postoperative Month 3 ± 7 days (Visit 5) - Interventional Arm

Evaluate symptoms and conduct a physical examination in alignment with ESMO guidelines (interventional treatment):

To mitigate the likelihood of participants experiencing unfavourable outcomes, we have implemented precautionary measures. Participants in the interventional arm are required to have clinical examinations every three months following surgery to remove the primary vulvar tumour. This requirement persists for a duration of 12 months. Ideally, participants will be scheduled to undergo their physical examination on-site. However, for those who reside far away and cannot return every three months, they can alternatively arrange an appointment with their local gynaecologist. A signed and de-identified visit report must be uploaded to REDCap within 5 working days, where QCGC Research will verify the completion of the clinical examination.

If any concerning indicators are detected, the participant will be referred to either the local PI or the specialist gynaecological oncologist to discuss their options. Depending on the clinical judgment of the clinician, the participant may be recommended for LND (standard treatment) or may opt to continue with bilateral groin ultrasound every two months and clinical examinations every three months (remaining on trial). Participants undergoing LND will no longer need bilateral groin ultrasound and blood collections every two months and clinical examinations every three months. However, their data will still be collected up to the original 12-month point. Data collected will include documentation of the status of disease, AEs, pain level, health status, quality of life, and lymphoedema.

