| Study Objectives | 
Primary objective:
 
 To determine the incidence of palpable, fixed to skin and histologically positive groin nodes at 12 months in women with vulvar cancer randomised to serial high-resolution groin USM versus standard surgical groin LND 
Secondary objectives:
 
 Compare Patient Reported Outcomes (PROMS) and Health-Related Quality of Life (HRQL) between the groups Compare pain and adverse events (morbidity) between the groups Compare lower limb lymphoedema between the groups Compare cost and cost effectiveness between the groups Determine the diagnostic accuracy of pre-operative, standardised high-resolution groin ultrasound to identify groin node metastasis. 
Translational research objective:
 
 To assess the role of blood and tissue molecular biomarkers to accurately determine the burden of disease (positive lymph nodes) in vulvar cancer, assist with risk stratification and aid disease surveillance |
| Study Endpoints | 
Primary endpoint:
 
 Incidence of clinically palpable, fixed to skin and histologically positive groin lymph nodes (node metastasis) at 12 months after surgical excision of the primary vulvar tumour |

| | |

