5.1 Primary Research Question

Is incidence of groin metastases (defined as enlarged, clinically palpable, fixed to skin and histologically positive nodes) comparable between women randomised to serial groin USM or upfront groin LND?

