5.3 Primary Objective

Determine the incidence of palpable, fixed to skin and histologically positive groin nodes in women with vulvar cancer randomised to serial high-resolution groin USM compared to standard upfront surgical groin LND at 12 months.

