An overall assessment will be made by the radiologist into normal or suspicious/positive. Radiologists will send their report to the local PI within 5 working days of ultrasound completion. All sites are required to enter the completed ultrasound eCRF on REDCap within 5 working days of ultrasound completion. Additionally, they must upload a copy of a signed and de-identified ultrasound report to REDCap, where QCGC Research will verify ultrasound completion.

If the participant is randomised to serial groin USM, patients will have surgical excision of the primary vulvar tumour followed by bilateral groin ultrasound every two months and clinical examinations every three months for the 12 months.

If suspicious, indeterminate, or positive nodes or any other concerning indicators are detected, the participant will be referred to either the local PI or the specialist gynaecological oncologist to discuss their options. Depending on the clinical judgment of the clinician, the participant may be recommended for LND (standard treatment) or may opt to continue with bilateral groin ultrasound every two months and clinical examinations every three months (remaining on trial). Participants undergoing LND will no longer need bilateral groin ultrasound and blood collections every two months and clinical examinations every three months. However, their data will still be collected up to the original 12-month point. Data collected will include documentation of the status of disease, AEs, pain level, health status and quality of life and lymphoedema. Please refer to section [10.6.5.1](#), titled 'Evaluating and Reporting Positive Nodes', for further information.

Patients that fail to comply with the serial ultrasound and clinical examination schedule will be removed from the trial and referred back to their gynaecological oncologist for alternative treatment for safety reasons.

7. Project Methodology

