7.5 Follow-Up (Visits 4-9)

All enrolled participants, irrespective of treatment group will be followed-up for 12 months. Participants without groin LND will be provided with medical imaging request forms to receive groin ultrasound examinations every 2 months. **Changes in ultrasound patterns from “normal” to “suspicious” will alert the gynae-oncologist and trigger further clinical action, such as groin LND and histological assessment of the groin nodes. Groin USM will not be offered to women who had a groin LND (IFL or SNB) as it is not standard practice for these patients.** If ultrasound scan surveillance following sentinel node biopsy is included in the standard care protocol at any of the study sites, participants randomised to lymph node dissection (LND) can undergo ultrasound scans as part of their standard care, though it is not mandatory for this study.

Participants will be assessed for local, regional, or distant recurrence, quality of life status, and treatment morbidity for 12 months. Data collected will include documentation of the status of disease, AEs, pain level, health status, quality of life and lymphoedema.

Participants randomised to serial groin USM will be seen every 3 months by a gynaecological oncologist or gynaecologist for clinical examination as per routine standard. Participants receiving standard groin LND (either SNB or LND) will be seen at 8 weeks, 3, 6, 9 and 12 months as per standard clinical practice. Follow up will be handed over to the treating gynaecological oncologist after 12 months.

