10.6.5.1 Evaluating and Reporting Positive Nodes

The senior medical imaging specialists will review the serial high-resolution bilateral ultrasound scans, evaluating for the presence of positive lymph nodes or any suspicious findings, relying on their clinical expertise. Radiologists will send their report to the local PI within 5 working days of ultrasound completion. All sites are required to enter the completed ultrasound eCRF on REDCap within 5 working days of ultrasound completion. Additionally, they must upload a copy of a signed and de-identified ultrasound report to REDCap, where QCGC Research will verify ultrasound completion. All sites should also provide a copy of de-identified US images to QCGC Research through The University of Queensland Research Data Manager platform (UQRDM) for quality assurance purposes. UQRDM is a secure platform designed for storing, managing, and sharing research data. It ensures compliance with data protection regulations and facilitates efficient data access and collaboration among researchers.

As explicitly stated in section [6.5.3](#) of the protocol, if suspicious, indeterminate, or positive nodes or any other concerning indicators are detected, the participant will be referred to either the local PI or the specialist gynaecological oncologist to discuss their options. Depending on the clinical judgment of the clinician, the participant may be recommended for LND (standard treatment) or may opt to continue with bilateral groin USM every two months and clinical examinations every three months (remaining on trial).

Participants receiving interventional treatment (serial groin USM in conjunction with clinical examination) who develop suspicious, indeterminate, or positive nodes are not removed from the trial as we still collect their data. The requirement for bi-monthly bilateral ultrasound, physical examination and blood tests will be discontinued.

11. Statistical Considerations

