11.2.9 Disease-Free and Overall Survival (DFS, OS)

Participants will be followed for 12 months and assessed for local, regional, or distant recurrence. Participants will be seen every 3 to 6 months. Clinical assessments will be performed at each visit. Clinical assessment, radiological work-up ± histological confirmation of recurrence will prove the presence of recurrent disease.

DFS is defined as time until the first recurrence or death from any cause. In patients without recurrence, or lost to follow-up, DFS will be censored on the date of the last follow-up visit. DFS will be compared between treatment arms using methods for the analysis of censored data. Variables to be evaluated for effect on DFS will include clinical management group (groin LND, ultrasound groin surveillance), age, medical comorbidities.

12 Trial Monitoring and Oversight

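### The primary event requires histology in three places and not in three others, and nothing fixes how a clinically evident groin failure without tissue is classified

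*Protocol*

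**What the plan says.** **Definitions that require histology.** The synopsis endpoint is "Incidence of clinically palpable, fixed to skin and histologically positive groin lymph nodes (node metastasis) at 12 months". Section 5.1 speaks of groin metastases "defined as enlarged, clinically palpable, fixed to skin and histologically positive nodes". The objective in 5.3 is to "Determine the incidence of palpable, fixed to skin and histologically positive groin nodes in women with vulvar cancer".

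**Definitions that do not state it.** Section 5.5, headed Primary Endpoint, refers to enlarged nodes that can be felt on examination and mentions neither fixation nor histology. Section 11.1, which sets the safety and stopping rules, models incurable groin recurrence within 12 months. Section 11.2.1 estimates the proportion of women with enlarged palpable groin node metastases.

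**What follows a finding in the USM arm.** Section 6.5.3: "If suspicious, indeterminate, or positive nodes or any other concerning indicators are detected, the participant will be referred to either the local PI". The alternative named there is a gynaecological oncologist, and in either case the purpose is a discussion of options. Section 7.5.2 adds that, at the clinician's judgement, "the participant may be recommended for LND (standard treatment) or may opt to continue with bilateral groin ultrasound every two months". Section 7.5 says a change to suspicious will "trigger further clinical action, such as groin LND and histological assessment of the groin nodes", so histology is given there as an example. Section 10.6.5.1 repeats the option to continue and then says of women who develop such nodes: "The requirement for bi-monthly bilateral ultrasound, physical examination and blood tests will be discontinued".

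**Recurrence for disease-free survival (DFS).** Section 11.2.9: "Clinical assessment, radiological work-up ± histological confirmation of recurrence will prove the presence of recurrent disease". Histology is optional.

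**Adjudication.** Section 12.5 sets up a blinded committee that reviews every reported recurrence, every six months from year 2.

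**The concern.** A safety verdict needs an event that every reader would count in the same way. Here two wordings of the event separate on one class of patient: a woman with a clinically evident groin failure from whom no node tissue is taken. The protocol allows this to happen, since no section mandates tissue, and the optional histology in 11.2.9 foresees recurrences without it.

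The disagreement has a direction. Under the histology wording an unsampled failure can only reduce the count. In the USM arm that moves the estimate towards an acceptable-safety declaration and away from the stopping bounds, which use the same count. It is plausible that frail women, women with advanced disease and women who decline surgery are sampled less often, but that is an inference and the protocol does not say so. If the governing wording is settled only once cases are known, the choice could decide the trial's conclusion.

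**Working it through.** **1. The definitions applied to one case.** Take a USM woman with an enlarged, palpable, skin-fixed groin node at month 9, with imaging that supports recurrence and no tissue taken by month 12.

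| Place | Histology stated? | Classification |
|---|---|---|
| Synopsis, 5.1, 5.3 | Yes | Not an event |
| 5.5 | No | Event |
| 11.1 | No | Event if judged incurable |
| 11.2.1 | No | Event if the node is called a metastasis |
| 11.2.9 (DFS) | Optional | DFS event |

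The same woman can be a DFS failure and a primary-endpoint success.

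**2. Reproducing the design.** Inputs from 11.1: safety threshold 0.06; declare safe at 80% posterior probability; stop above 70% posterior probability of exceeding 0.06, at 5/40, 6/60, 7/80, 9/100 or 10/120; assumed true rate 3%; prior informed by 1/32, weight not stated. The model is Beta(a, b) updated to Beta(a+x, b+n−x).

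- Beta(0.5, 15.5), which is the pilot at half weight, and Beta(1.5, 31.5) each reproduce all five stopping bounds.
- Both give success at 5 or fewer events in 120.
- At a true 3%, exact recursion over looks at 40, 60, 80, 100 and 120 gives P(stop) = 0.018 (stated: below 2%) and P(declare safe) = 0.847 (stated: 0.85).
- Full-weight Beta(1, 31) does not match: it passes at 6 or fewer and gives 0.928.

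**3. How close the verdict is.** Posterior probability that the rate is below 0.06:

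| Events/120 | Beta(0.5, 15.5) | Beta(1.5, 31.5) | Result |
|---|---|---|---|
| 5 | 0.874 | 0.859 | Declared safe |
| 6 | 0.770 | 0.758 | Not declared safe |

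One event classified differently reverses the verdict.

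**4. Illustrative effect of uncounted events.** Let p be the true rate and u the share of true events that lack tissue and are not counted. The observed rate is p(1−u). For example, 0.06 × 0.8 = 0.048 and 0.08 × 0.8 = 0.064. The bounds and pass mark are those of step 2. The protocol gives no value for u, so a range is shown.

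| True p | u | Observed rate | P(declare safe) | P(stop) |
|---|---|---|---|---|
| 6% | 0 | 6.0% | 0.27 | 0.29 |
| 6% | 10% | 5.4% | 0.37 | 0.21 |
| 6% | 20% | 4.8% | 0.48 | 0.14 |
| 6% | 30% | 4.2% | 0.61 | 0.08 |
| 6% | 50% | 3.0% | 0.85 | 0.02 |
| 8% | 0 | 8.0% | 0.075 | 0.60 |
| 8% | 10% | 7.2% | 0.13 | 0.48 |
| 8% | 20% | 6.4% | 0.21 | 0.35 |
| 8% | 30% | 5.6% | 0.33 | 0.23 |
| 8% | 50% | 4.0% | 0.65 | 0.07 |

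**5. Limit on the remedy.** Counting every groin recurrence acceptable under 11.2.9 would bring in small nodes found by ultrasound. In the pilot (section 3.4) there were 3 such positive nodes in 32 women, 3/32 = 9.4%, against the 1/32 used in 11.1. With n = 120, P(5 or fewer) is 0.03 at 9.4%, compared with 0.85 at 3%. Such a rule would measure a different outcome from the one to which the 3% and 6% figures refer.

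**The case against.** The sections that set the verdict (11.1 and 11.2.1) and the formal endpoint (5.5) do not require histology, and no sentence says that missing histology means no event. A reader might infer that unsampled groin failures will be scored as event-free in the 6% rule. The documents do not support that as a statement of what will happen; it follows only if the synopsis wording governs.

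A concerning indicator or suspicious scan is also not the primary event. A woman who continues monitoring stays under ultrasound and examination, later tissue is not barred, and 7.5 names histology among the expected actions. It would be wrong to say that she can never become an event. The blinded committee sees each reported recurrence and could count a case without tissue. Finally, 11.2 defers detail to a statistical analysis plan under the estimand framework, which is not at hand, and the shares in step 4 have no source in the protocol.

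These points limit the size and certainty of the concern, but the contradiction remains. Section 12.5 asks the committee for the location and date of a recurrence; it gives no rule for cases without tissue and does not tie the committee to the primary endpoint. An analysis plan can choose between two protocol definitions, but the protocol would still contain both.

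**Conclusion.** The point holds as an inconsistency in the primary event, with a possible bias in one direction. The synopsis, 5.1 and 5.3 make a clinically evident but unsampled groin failure a non-event; 5.5, 11.1 and 11.2.1 do not require that reading. If the histology wording governs, the USM count can only fall, and a single case separates pass from fail under both priors that reproduce the protocol's bounds.

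The reversal between 5/120 and 6/120 rests on the protocol's own thresholds and on a prior weight inferred from its bounds. The larger movements (0.27 to 0.48 at a true 6%, and 0.075 to 0.21 at a true 8%, with 20% uncounted) are illustrations. They rest on an assumed share and on the histology wording governing the safety rule. This should be corrected before the safety count is relied on.

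**What to change.** Use one event definition in 1.1, 5.1, 5.3, 5.5, 11.1 and 11.2.1, and in the stopping count. State the following with it:

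- A groin failure that meets the clinical part of the definition (palpable and fixed, the incurable recurrence that 11.1 models) but has no tissue counts as an event unless histology or cytology is negative.
- The existing blinded adjudication committee rules on these cases, in both randomised arms.
- Non-palpable nodes detected by ultrasound do not count.
- The histology-confirmed count is reported as a sensitivity analysis.

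The cost is wording in the protocol and analysis plan, and a line in the committee's terms of reference. No extra biopsy is needed. The USM rate may come out slightly higher.

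Separately, 6.5.3, 7.5, 7.5.2 and 10.6.5.1 describe what follows a suspicious finding in ways that do not agree: action triggered, continuation at the clinician's judgement, or monitoring discontinued. They must be reconciled; no clinical rule is proposed here.

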5.6 Secondary Endpoint

1. HRQL and PROMS as measured by the EQ-5D and FACT-V at baseline, 8 weeks, 6 months, and 12 months
2. Morbidity at 12 months after surgery
3. Lower limb lymphoedema: incidence up to 12 months after surgery
4. Cost and cost effectiveness at 12 months post-surgery
5. Clinical accuracy of high-resolution ultrasound to predict groin lymph node involvement
6. Disease-free survival (DFS) and overall survival (OS)
7. Utility of biomarkers to reliably reflect the presence or absence of positive groin lymph nodes
8. Explore novel biomarkers for vulvar cancer

6. Study Design

A phase II, open label, multicentre, three-group, randomised clinical trial (ANVU).

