7.5.1 Postoperative Week 8 ± 3 days (Visit 4) - All Participants

Can be obtained via medical visit, telephone contact or postal correspondence:

- Provide participant with booklet containing PROMS, HRQL and lymphoedema questionnaires
- Lymphoedema assessments via BIS and leg circumference measurements (participating sites only) and/or Self-Report Questionnaire
- Review ECOG performance score
- Assess participants for their individual pain level using Numeric Pain Rating Scale
- Record disease status
- Collect all AEs (assess using Common Terminology Criteria for Adverse Events (CTCAE) V5.0)
- Record hospitalisations
- Record FBC, Urea and Electrolytes and LFT's if available
- Collect all serious adverse events (SAEs)
- Update new medications since surgery

- Optional post-operative translational research blood collection for all consented participants
- Serial high-resolution groin ultrasound (interventional treatment)
- Evaluate symptoms and conduct a physical examination in alignment with European Society for Medical Oncology (ESMO) guidelines.

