11.2.3 Morbidity of Intervention

Post-surgery, patients will be assessed daily until discharge from hospital. Perioperative outcomes including duration of surgery (time from skin incision to wound closure), length of hospital stay,

estimated intraoperative blood loss, requirements for blood transfusions, intraoperative complications, and crossovers (including the clinical necessity for a comprehensive LND) will be recorded. Intraoperative injuries, postoperative AEs and SAEs will be recorded according to the CTCAE V5.0, at predefined time points for up to 12 months. We will compare the incidence of (a) intraoperative; (b) postoperative; and (c) serious AEs at 8 weeks and 6 months and 12 months post-surgery.

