11.2.6 Cost and Cost Effectiveness

Health resources utilised between study groups will be identified, measured, and valued to obtain the total costs of each intervention. Length of stay and subsequent hospital admissions up to 12 months post-surgery will be valued (national hospital pricing model) and prices adjusted based on 3% annual inflation. The use of all health services (including adjuvant treatments) within 12 months of surgery will be collected and valued at each site in \$AUD. Cost of AEs will be allocated depending on their severity as determined using the CTCAE V5.0. To assess the value of health outcomes for each surgical option, the EQ-5D-5L will be used to estimate utility scores and calculate gains in quality adjusted life years (QALYs) associated with the intervention.

A Markov model will simulate how patients progress through health states and incur costs and QALYs. Model input parameters (e.g., transition probabilities, costs, and utility scores) will be obtained from this trial and other relevant published literature. The incremental costs and QALYs will be compared to calculate the incremental cost effectiveness ratio (ICER). A willingness to pay threshold of \$50,000/QALY, a commonly used threshold in the literature, will be used as a decision rule [46]. Probabilistic sensitivity analysis will be conducted to characterise the uncertainty in the results of the economic evaluation. Value of implementation analysis will be conducted to estimate the expected net health and monetary benefits gained with the adoption of groin node ultrasound surveillance.

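### Women who move from ultrasound monitoring to a delayed LND are followed only to month 12 from the first surgery, so the lasting burden of delayed LND is only partly observed

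*Protocol*

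**What the plan says.** - **Follow-up.** Section 7.5 states "All enrolled participants, irrespective of treatment group will be followed-up for 12 months" and "Follow up will be handed over to the treating gynaecological oncologist after 12 months". For a USM participant who has LND, Section 7.5.2 adds "However, their data will still be collected up to the original 12-month point"; Section 6.5.3 has the same sentence. No section starts a new schedule at the delayed LND. Longer follow-up appears only among the post-trial options in Section 4, for survival.
- **Lymphoedema.** Section 5.6 lists "Lower limb lymphoedema: incidence up to 12 months after surgery". Sections 8.3 and 8.3.1 place the assessments at baseline, 8 weeks, 6 months and 12 months after surgery.
- **Surveillance.** The first USM scan and examination fall at the visit headed "7.5.1 Postoperative Week 8 ± 3 days (Visit 4) - All Participants". Later scans are at months 4, 6, 8, 10 and 12.
- **Adverse events.** AEs run to 12 months. Sections 10.2, 10.3 and 10.4 and the Section 16 schedule end SAE collection at 6 months after surgery. Section 11.2.3 nevertheless has SAEs recorded up to 12 months and plans to compare "serious AEs at 8 weeks and 6 months and 12 months post-surgery".
- **Cost.** Section 11.2.6 values health services used within 12 months of surgery and adds a Markov model: "Model input parameters (e.g., transition probabilities, costs, and utility scores) will be obtained from this trial and other relevant published literature".

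**The concern.** Delayed LND is a planned part of the USM strategy. Section 2 says LND will be needed for the few women in whom ultrasound detects metastasis. In the LND arm the dissection is done at the vulvar surgery (Section 7.4), so every woman has 12 months of observation after it. A USM woman who switches has her dissection later and is observed only for what remains of the same 12 months.

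Aim 2 in Section 5.2 is that USM decreases morbidity, and Section 3.3 describes lymphoedema as life-long. Section 6.5.2 provides for radiation in specified node-positive cases, so some switchers may carry the heavier treatment. The decision tool in Section 8.5 weighs nodal recurrence under USM against lymphoedema and morbidity under LND. A woman choosing USM also needs to know what a delayed LND would bring, and the trial will see that only in part. A statistical analysis plan can define estimands, but it cannot recover data that were never collected.

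**Working it through.** The protocol gives no figure for this point. Its only design calculation (Section 11.1) concerns groin recurrence and is unaffected. With an assumed Beta(1.5, 31.5) prior, since the prior parameters are not stated, it reproduces: all five stopping boundaries, a 0.847 probability of declaring safety at a true 3%, and 1.7% false early stopping.

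**Observation after a delayed LND.** Months left = 12 minus the time of the triggering scan. For week 8: (365 − 56)/30.44 = 10.2. SAE cover left for week 8, on the 6-month limit: (183 − 56)/30.44 = 4.2. The lag column assumes one month from scan to surgery.

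| Triggering scan | Months left, no lag | Months left, one-month lag | Lymphoedema assessments left | Months of SAE cover left, no lag |
|---|---|---|---|---|
| Week 8 | 10.2 | 9.2 | 2 | 4.2 |
| Month 4 | 8 | 7 | 2 | 2 |
| Month 6 | 6 | 5 | 1 | 0 |
| Month 8 | 4 | 3 | 1 | 0 |
| Month 10 | 2 | 1 | 1 | 0 |
| Month 12 | 0 | 0 | 0 | 0 |
| LND arm | 12 | 12 | 3 | 6 |

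If detection is spread evenly over the six scans (an assumption), the mean is 30.2/6 = 5.0 months without lag and 25.2/6 = 4.2 months with it, against 12. A switch triggered by the month 3 or month 9 examination would leave at most 9 or 3 months.

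**Number of switchers.** Section 3.4 reports 3 positive nodes in 32 pilot patients, all within 12 months, and 29 spared LND.
- 3/32 × 120 = 11.25, so about 11 women.
- The exact 95% interval for 3/32 is 2.0% to 25.0%, which gives about 2 to 30 women.

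**Ceiling for lymphoedema.** Section 3.3 quotes 60% after LND.
- All switcher cases missed: 0.60 × 11.25 = 6.75 women, and 6.75/120 = 5.6 points (1.2 to 15 points over the interval).
- Half missed: 2.8 points.

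**Wholly unseen under even detection.**
- Month-12 triggers only: 11.25/6 × 0.60 = 1.1 cases, or 0.9 points.
- Month-10 triggers also counted as wholly missed: 2 × 1.125 = 2.25 cases, or 1.9 points.

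**The case against.** The strongest reply is that nothing is wrong with the planned comparison. Both arms are followed for the same 12 months from the first surgery, analysis is by intention to treat (Section 11.2), and the endpoint is defined on that window. A policy of immediate LND against one of deferred or avoided LND is a legitimate 12-month contrast. This stands. A reader might infer that the follow-up clock biases the trial's comparison in favour of USM. The protocol does not support that, because it never takes time since LND as its denominator.

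A reader might also infer that the Markov model will carry truncated delayed-LND rates forward. Section 11.2.6 describes no delayed-LND state, states no model horizon and allows published inputs. Bias in cost-effectiveness is possible, not shown.

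On size, one could add a pilot false positive and reach 4/32 × 120 = 15 switchers and 7.5 points. The pilot text does not support this, since 29 of 32 were spared LND. The trial's own rate could still be higher than 3/32, because Section 6.5.3 lets suspicious or indeterminate scans lead to LND.

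Early complications are largely covered. AEs and hospitalisations are collected at months 4, 6, 8, 10 and 12, and Section 10.6.4 follows ongoing events for up to 30 days after the 12-month visit. That covers events close to the operation, but not lymphoedema developing later, and not events that begin after month 12.

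**Conclusion.** The point holds as a gap in data collection. USM women who later have LND are observed for 0 to about 10 months after it (mean about 4 to 5 under even detection) against 12 months in the LND arm, with at most two of the three lymphoedema assessments. The 12-month comparison is valid for what it measures, but it understates the lasting burden of delayed LND in the USM strategy.

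The size is modest: about 11 of 120 women (2 to 30 over the exact interval), a ceiling of 5.6 points of lymphoedema incidence, and about 1 to 2 points wholly unseen. This rests on the pilot's 3/32 as the switch rate, 60% lymphoedema after delayed LND, and even detection over six scans. It is small beside the 60% quoted for LND and unlikely by itself to reverse the conclusion on aim 2.

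The SAE window is a separate inconsistency. If sites follow Section 10 and the schedule, a serious complication of an LND done after month 6 is not captured as an SAE, although Section 11.2.3 compares serious AEs at 12 months. These sections need to be reconciled.

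**What to change.** Keep the comparison at 12 months from first surgery as the main analysis, and make these changes:

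1. In Sections 6.5.3 and 7.5.2, add that a USM participant who has LND repeats the lymphoedema, FACT-V and EQ-5D booklets and AE/SAE collection at 8 weeks, 6 months and 12 months after that LND, by post or telephone, even past the original month 12. Make the matching exception to the handover in Section 7.5.
2. Extend SAE collection to 12 months for all groups in Sections 10.2, 10.3 and 10.4, the month 8, 10 and 12 visit lists and the Section 16 schedule, to agree with Section 11.2.3.
3. Report delayed-LND morbidity by time since LND as a supplementary descriptive analysis. Use it in the decision tool and as a sensitivity input to the Markov model.

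The cost is up to about 12 months of extra remote follow-up for about 11 women, using contact modes the protocol already allows, plus an amendment and a later supplementary report. The main analysis need not wait, but any update of the decision tool or the sensitivity model that uses these data would. Estimates will be imprecise: 7 cases in 11 women would have an exact 95% interval of about 31% to 89%. The amendment should be in place before switchers reach month 12, since the data are hard to recover afterwards.
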